
	
retrospective study] that doesn't affect this study's efficacy and safety as determined by the investigator.)
 
[Laboratory tests]
 
12) At screening, those who had
 
 ① serum alanine aminotransferase (ALT), aspartate aminotransferase (AST), or total bilirubin levels ≥ 2 X upper limit of normal ② serum creatinine or BUN ≥ 2 X upper limit of normal 
[Others]
 
13) Pregnant or breast-feeding women
 
14) Those who do not consent to use appropriate contraceptive methods during the study.
 
 - Appropriate contraceptive methods for patients or their partners - For Male subject: to use barrier method such as male condom and surgical sterilization such as vasectomy - For Female subject: to use 1) hormonal contraceptive such as Intrauterine system : intrauterine hormone-containing system, implant, injection, contraceptive pills, or 2) non hormonal contraceptive such as Intrauterine system : copper loop, barrier method : female condom, diaphragm or cervical cap, or surgical sterilization : tubectomy. 
15) In the opinion of the investigator, those who were unsuitable for any reason.

Investigational product and mode of administration	
[Investigational Product]
 
 ● Study drug: Fexuprazan tablet 40 mg ● Control drug: Esomeprazole capsule 40 mg 
[Treatment period]
 
 ● Treatment 1: 4 weeks A dose of Study drug or Control drug will be administered orally once daily without regard to meals for 4 weeks. The timing of administration should be kept consistent for each subject. ● Treatment 2: Up to 8 weeks (4 weeks + 4 weeks) Patients who have not been healed after the Treatment 1 of investigational product administration will have an additional 4-weeks of treatment period (Treatment 2) with the same mode of administration. Patients that categorized as a non-healed are those with a GERD-Q score >8.

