5.1 Scheduled Completion

If all protocol-specified procedures and assessments are completed after the IP administration, the subject will be considered to have completed the study. Subjects with symptoms relief at Week 4 measured by GERD-Q Score <8 will have the Safety F/U after 2 weeks from the date and be terminated from the study.

In this study, completion of the last subject is defined as the end of study.

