- 7) Laboratory tests will be conducted to check the inclusion/exclusion criteria and assess the safety (Visit 1, Visit 4, Visit 5, Withdrawal visit, and Safety F/U). At Visit 1, a re-test may also be conducted once according to the investigator's judgment and, in such a case, evaluation will be based on the results of re-test.

① Hematology	WBC with differential count (neutrophil, lymphocyte, monocyte, eosinophil, basophil), RBC, hemoglobin, hematocrit, platelets
② Blood Chemistry	Random blood glucose, ureum, uric acid, AST, ALT, creatinine, total bilirubin
③ Blood Coagulation test	PT, INR, APTT
④ Urinalysis	pH, specific gravity, albumin, bilirubin, glucose, urobilinogen, ketone, nitrite, occult blood, microscopy (urine RBC, urine WBC)

- 8) Pregnancy test will be performed with serum or urine pregnancy test will be performed at Visit 1. (Women who medically do not have child-bearing potential are exempt from the pregnancy test). If Visit 1 and Visit 2 are conducted on the same day, another pregnancy test (serum or urine test) should be conducted prior to IP administration even if the test result within 2 weeks before the date is available.
- 9) Eligibility of subjects will be assessed based on the results from Visit 2 (However GERD-Q result from Visit 1 will be used as the eligibility criteria).
- 10) Subjects who have not symptoms relief at Visit 4 will be prescribed the investigational product for treatment 2, and

subject diary will be distributed to them. At Visit 5, treatment compliance will be checked, and subject diary will be collected only from those who have undergone Treatment 2.

(#: Subject diary completion will be checked at Visit 3, and appropriate training on diary keeping will be performed on the phone, if necessary.)

- 11) The Safety F/U will be conducted as a telephone visit within 2 weeks (\pm 5 days) from Visit 4 only in subjects who complete all protocol-specific treatments, and the subjects may visit for additional tests or treatments based on the investigator's judgment.

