8.3.14 Distribution and Collection of Subject Diary

The subject diary will be distributed at Visit 2 and the training on how to complete it will be provided. The completion status of the subject diary will be checked at Visit 3 via site visit, and appropriate training on the diary keeping will be performed, if necessary. At Visit 4, the completed subject diary will be collected and the subjects who have not symptoms relief will be prescribed the IP for Treatment 2 and the subject diary will be re-distributed to the subject. At Visit 5, the subject diary will be collected only from those who have undergone Treatment 2. Assessment of symptoms and treatment compliance will be done based on the subject diary

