8.4.1.2 Secondary Efficacy Endpoints

1. Proportions of subjects with symptoms relief at week 8 measured by GERD-Q Score <8
(Week 8 evaluation will only be applicable to patient receiving treatment 2)

2. Assessment on symptoms based on the diary of subjects

- The day to reach complete response (disappearance of heartburn, acid regurgitation, or heartburn/acid regurgitation for 7 consecutive days) after the first IP administration.
- Proportions of subjects without the major symptoms (heartburn, acid regurgitation, or heartburn/acid regurgitation) for first 7 days, 4 weeks, and 8 weeks after the first IP administration.
- Proportions of days free of major symptoms (heartburn, acid regurgitation, or heartburn/acid regurgitation) for first 7 days, 4 weeks, and 8 weeks after the first IP administration (including all daytime, nighttime, and daytime/nighttime)
- However, the secondary efficacy endpoints will only be assessed in patients who are not healed with treatment 1 and will continue to receive safety and rescue.

(Week 8 evaluation will only be applicable to patient receiving treatment 2)

3. Assessment on symptoms of reflux disease (GERD-Q)

- Changes from baseline in frequency by major symptom after 7 days, 4 weeks and 8 weeks.
(Week 8 evaluation will only be applicable to patient receiving treatment 2)

4. Assessment of Quality of Life (GERD-HRQL: GERD-Health related quality life)

- Changes from baseline in the total score of GERD-HRQL after 7 days, 4 weeks and 8 weeks.
(Week 8 evaluation will only be applicable to patient receiving treatment 2)

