9.2.3.2 Secondary Efficacy Assessment

1. Proportions of subjects with symptoms relief at week 8 measured by GERD-Q Score <8

The proportions of subjects with symptoms relief by Week 8 and their 95% confidence intervals will be provided by group. The proportions of subjects with symptoms relief by Week 8 will be calculated as the cumulative symptoms relief by using the results at the time of final observation including the Withdrawal visit. To compare the control group and study group, the lower bound of the 2-sided 95% confidence intervals will be obtained by using the Chi Square test or Fisher's Exact test method. If this lower bound is greater than the non-inferiority margin of -0.1, the study group will be judged to be non-inferior to the control group. (Week 8 evaluation will only be applicable to patient receiving treatment 2)

2. Assessment on symptoms based on the diary of subjects

- CR (disappearance of heartburn, acid regurgitation, or heartburn/acid regurgitation for 7 consecutive days) is defined as the symptom score of 0 for 7 consecutive days for the first time after the first dose, and the survival time is defined as the time to reach Complete Response (CR) after the first IP administration. Kaplan-Meier plots will be drawn by treatment group, and the medians and their 2-sided 95% confidence intervals will be presented. To compare the control group and study group, the log-rank test will be used.
- The number of subjects without any heartburn, acid regurgitation, or heartburn/acid regurgitation for the first 7 days, full 4 weeks, and full 8 weeks from the first IP administration, the proportion (%) of these subjects and its 95% confidence interval will be presented by treatment group. To compare the control group and study group, the 2-sided 95% confidence intervals and p-value will be obtained by using the Chi Square test or Fisher's Exact test method.

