Attachment 2. Gastroesophageal Reflux Disease Questionnaire (GERD-Q)

Screening No.	__S__	Subject No.	__R__			
Subject initial						
Visit No.	 Visit 1	 Visit 2	 Visit 3	 Visit 4	 Visit 5	 Early withdrawal or unscheduled visit

Cobalah mengingat apa yang Anda rasakan dalam 7 hari terakhir						
Berikan tanda centang (v) hanya pada satu tempat untuk setiap pertanyaan dan hitunglah poin GERD-Q Anda dengan menjumlahkan poin pada setiap pertanyaan.						
No.	Pertanyaan	Frekuensi dari skor (poin) untuk gejala				
		0 hari	1 hari	2-3 hari	4-7 hari	
1.	Seberapa sering Anda mengalami perasaan terbakar di bagian belakang tulang dada Anda (heartburn)?	 0	 1	 2	 3	
2.	Seberapa sering Anda mengalami naiknya isi lambung ke arah tenggorokan/mulut Anda (regurgitasi)?	 0	 1	 2	 3	
3.	Seberapa sering Anda mengalami nyeri ulu hati?	 3	 2	 1	 0	
4.	Seberapa sering Anda mengalami mual?	 3	 2	 1	 0	
5.	Seberapa sering Anda mengalami kesulitan tidur malam oleh karena rasa terbakar di dada (heartburn) dan/atau naiknya isi perut?	 0	 1	 2	 3	
6.	Seberapa sering Anda meminum obat tambahan untuk rasa terbakar di dada (heartburn) dan/atau naiknya isi perut (regurgitasi), selain yang diberikan oleh dokter Anda? (seperti obat maag yang dijual bebas)	 0	 1	 2	 3	
Hasil		Bila poin GerdQ Anda \leq 7, kemungkinan Anda tidak menderita GERD Bila poin GerdQ Anda 8-18 , kemungkinan Anda menderita GERD				

*) The Gastroesophageal Reflux Disease Questionnaire has been validated by Marcellus Simadibrata, Aziz Rani, Pangestu Adi, Ali Djumhana, Murdani Abdullah with an article titled “The gastro-esophageal reflux disease questionnaire using Indonesian language: a language validation survey” at May 2011.

Documented date	Date Month Year 20	Documented by	(Signature)

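### The combined-symptom version of the 8-week symptom-free proportion is assessed only in subjects selected for not having Week 4 relief, so it is expected to be near 0% in both arms

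*Combined protocol and SAP*

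**What the plan says.** Section 9.2.3.2, item 2, and the synopsis define a diary endpoint as "The number of subjects without any heartburn, acid regurgitation, or heartburn/acid regurgitation for the first 7 days, full 4 weeks, and full 8 weeks", starting at first dose. It has three versions: heartburn, acid regurgitation, and the two combined. Each is to be compared between arms with a 95% confidence interval and a p-value.

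The denominator at 8 weeks is restricted: "Week 8 evaluation will only be applicable to patient receiving treatment 2" (8.4.1.2, repeated at the end of item 2 in 9.2.3.2). Section 8.4.1.2 also carries a broader sentence under the diary endpoints: "However, the secondary efficacy endpoints will only be assessed in patients who are not healed with treatment 1".

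Entry to Treatment 2 depends on the Visit 4 GERD-Q. Footnote 10 in Section 8.2 says "Subjects who have not symptoms relief at Visit 4 will be prescribed the investigational product for treatment 2". Section 5.1 sends the others out of the study: "Subjects with symptoms relief at Week 4 measured by GERD-Q Score <8 will have the Safety F/U after 2 weeks". The synopsis words the entry rule differently: "Patients that categorized as a non-healed are those with a GERD-Q score >8".

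The GERD-Q form (Attachment 2) recalls one week: "Cobalah mengingat apa yang Anda rasakan dalam 7 hari terakhir". After Week 4 only Treatment 2 subjects have a diary: "At Visit 5, the subject diary will be collected only from those who have undergone Treatment 2" (8.3.14).

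**The concern.** The 8-week window runs from first dose and so contains the week that the Visit 4 GERD-Q recalls. Subjects who did well in that week leave at Week 4 and have no later diary. Those who stay were selected mainly because they had reflux symptoms in it. For the combined symptom, entering the denominator nearly implies having failed the numerator already.

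At stake is one time point of one secondary endpoint. The combined comparison would show roughly 0% against 0% almost regardless of what either drug does in Weeks 5 to 8. It could be read as no difference at 8 weeks, yet it would say nothing about whether the additional four weeks helped.

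**Working it through.** **1. Planning figures, reproduced first.** The documents give no figure for this endpoint, so its denominator has to come from the primary sample size. Inputs from Section 9.4.2: control relief 0.885, study relief 0.940, margin 0.1, one-sided 2.5%, 80% power, 1:1 allocation, pooled Z-test. With mean rate 0.9125:

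n = [1.960 × √(2 × 0.9125 × 0.0875) + 0.842 × √(0.885 × 0.115 + 0.940 × 0.060)]² / (0.1 + 0.055)² = 52.02, rounded up to 53 per arm. Power at 53 is 0.8073, against 0.80729 in the plan. With 20% dropout, 53 / 0.8 = 66.25, so 67 per arm and 134 in total. The plan's figures are reproduced.

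**2. Overlap of the two windows.** Visit 4 is Day 28 ± 5, so Day 23 to Day 33. The 7 days before it fall between Day 16 and Day 32, always inside the 8 weeks from first dose.

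**3. GERD-Q scoring (Attachment 2).** Each item scores 0 to 3. Items 1 (heartburn), 2 (regurgitation) and 5 (sleep disturbed by either) score 0 when the symptom is absent. Items 3 (epigastric pain) and 4 (nausea) are reversed and score 3 when absent. Item 6 counts days with extra reflux medicine beyond what the doctor gave: 2–3 days score 2, and 4–7 days score 3.

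For a subject with neither major symptom in the recall week, items 1 = 2 = 5 = 0. The maximum total is then:
- 3 + 3 + 0 = 6 with no extra medicine;
- 3 + 3 + 1 = 7 with extra medicine on 1 day;
- 3 + 3 + 2 = 8 on 2–3 days;
- 3 + 3 + 3 = 9 on 4–7 days.

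Of the 4³ = 64 answer patterns for items 3, 4 and 6, four reach 8 or more: (2,3,3), (3,2,3), (3,3,2) and (3,3,3). Only (3,3,3) exceeds 8. With item 6 at 0 or 1, none of the 32 patterns reaches 8.

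**4. Single-symptom versions.** With item 1 = 0 (or item 2 = 0) and no extra medicine, the maximum is 4 × 3 = 12, and 66 of 256 patterns reach 8 or more. These versions are not forced to zero.

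**5. Expected denominators.** Subjects entering Treatment 2 = n × (1 − relief rate).

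| n per arm | Control | Study | Total |
|---|---|---|---|
| 53 | 53 × 0.115 = 6.1 | 53 × 0.060 = 3.2 | 9.3 |
| 67 | 67 × 0.115 = 7.7 | 67 × 0.060 = 4.0 | 11.7 |

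These counts treat every score of 8 or more as entering. If relief were only 70% in an arm (assumption), about 16 to 20 subjects in that arm would enter.

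**6. What the comparison could show.** With no successes, the exact 95% upper limit is 1 − 0.025^(1/n): 60% for 0/4 and 37% for 0/8. Fisher's test with 4 study and 8 control subjects has power 0 if both true rates are 0. Power is below 0.4% if the rates are 10% study against 0% or 5% control (assumed).

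**7. No other rule fills the gap.** Last observation carried forward applies only to continuous endpoints (9.2.1). The cumulative-relief wording in 9.2.3.2 belongs to item 1, the GERD-Q endpoint.

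**The case against.** Several points on the other side are fair.

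- **Not the whole comparison.** A reader might infer that all three 8-week versions are fixed at 0% against 0%. Step 4 shows otherwise: heartburn-only and regurgitation-only success remain possible, though essentially only for subjects who failed Week 4 on something else.
- **Not exactly zero, and not a probability.** It is tempting to read 4 of 64 as a chance of about 6%. The patterns are not equally likely: absent epigastric pain and nausea are plausible on treatment. The count shows only which route is open, namely frequent extra medicine.
- **Two instruments.** The GERD-Q is a weekly recall and the diary is filled in twice daily. The daily diary page labels its heartburn row *nyeri ulu hati*, the term used in reverse-scored GERD-Q item 3, whereas the diary instructions define heartburn as burning in the chest. A subject reading the row as epigastric pain could score up to 12 on GERD-Q, with no regurgitation and no extra medicine, and still record a symptom-free diary. This loosens the link, but such a row would then not be measuring heartburn.
- **A low rate may be inherent.** In the phase 2 study (Section 1.4; erosive disease, a different population) only 21.57% on fexuprazan 40 mg and 12.50% on esomeprazole had no major symptoms for even the first 7 days. A low 8-week rate would be likely anyway, and the replacement endpoint may also be low. That does not make the present version informative.
- **Other endpoints cover Weeks 5 to 8.** Week 8 GERD-Q relief, symptom-free days and change in GERD-HRQL address that period, and the planned confidence intervals would reveal the imprecision. This limits the weight of the point. Those endpoints share the small denominator selected after randomization, a wider matter that this point does not settle.

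**Conclusion.** The point holds for the combined symptom. Its 8-week symptom-free proportion is expected to be near 0% in both arms because the denominator was selected on a score that, without extra reflux medicine on at least 2 of 7 days, requires a major symptom inside the endpoint's own window. About 6 control and 3 study subjects would be compared at 53 per arm (8 and 4 at 67), and the p-value carries no useful information.

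This rests on the planning relief rates, on the form's scoring, and on reasonable agreement between diary and GERD-Q. It does not depend on how the synopsis (above 8) and Section 5.1 (below 8) are reconciled for a score of exactly 8: four patterns remain under one cut-off and one under the other.

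The documents do not support extending the point to the primary endpoint or the sample size. Nor do they settle whether the 7-day and 4-week versions are affected. The broader sentence in 8.4.1.2, taken literally, would restrict those versions to unhealed subjects too, whereas the Week 8 notes limit only the 8-week evaluation.

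**What to change.** In the synopsis, 8.4.1.2 and 9.2.3.2 item 2:

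1. Replace the 8-week symptom-free proportion with the proportion having no major symptoms during Treatment 2, from the day after Visit 4 to Visit 5. Report it descriptively by arm among Treatment 2 subjects, without a between-arm p-value.
2. In the same edit, limit the 8.4.1.2 sentence ("However, the secondary efficacy endpoints will only be assessed in patients who are not healed with treatment 1") to the Week 8 time point, so that the 7-day and 4-week versions are analysed in all subjects. Without this, the text would still contradict itself.
3. Reconcile the synopsis and Section 5.1 on a GERD-Q score of exactly 8. Which rule applies is for the trial team to decide.

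The cost is wording only. The Treatment 2 diary already collects the data, and no visit, subject or procedure is added. The downside is that the replacement remains imprecise, with roughly 9 to 12 subjects in total at the planning rates.

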8.3.3 Questionnaire assessment

- Gastroesophageal Reflux Disease Questionnaires (GERD-Q) (See Appendix 3)
 - The subject will complete the GERD-Q at the screening visit (Visit 1) and Visit 2. The test results from Visit 1 will be used as the basis to determine eligibility for inclusion/exclusion.
 - The subjects who meet the inclusion criteria will complete the GERD-Q at Visit 3, Visit 4, and Visit 5.
- Quality of Life assessment (GERD-Health Related Quality of Life, GERD-HRQL) (See Appendix 4)
 - The subjects who meet the inclusion criteria will complete the GERD-HRQL questionnaire at Visit 2, Visit 3, Visit 4 and Visit 5.^[19, 20, 21]

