8.3.13 Investigational product administration

For maximum 8 weeks from the next day of investigational product dispensing, 1 tablet/capsule will be administered orally once daily without regard to meals. Tablets/Capsules should be taken at a regular time, if possible. At each visit after the administration of the IP all subjects should return the unused IP prescribed at the previous visit and empty packaging.

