- Descriptive statistics (mean, standard deviation, median, minimum, and maximum) of the proportions of days free of any heartburn, acid regurgitation, or heartburn/acid regurgitation for the first 7 days, full 4 weeks, and full 8 weeks from the first IP administration will be presented for daytime, nighttime, and daytime/nighttime by group. For comparison between treatment groups, an ANCOVA model will be applied with treatment group as a treatment effect. The results of ANCOVA model will be summarized as the LSM differences between the study group and the control group, the corresponding 2-sided 95% confidence interval, and p-value.
(Week 8 evaluation will only be applicable to patient receiving treatment 2)

3. Assessment on symptoms of reflux disease using GERD-Q

Descriptive statistics (mean, standard deviation, median, minimum, and maximum) for the changes from baseline in frequency at the first 7 days, 4 weeks, and 8 weeks will be presented by time point. For the changes from baseline in variables measured at the first 7 days, 4 weeks, and 8 weeks after the IP administration, an ANCOVA model including treatment group as treatment effect, and baseline value will be applied. The results of ANCOVA model will be summarized as the least squares mean (LSM) and standard error by treatment group, the LSM differences between the study group and the control group, the corresponding 2-sided 95% confidence interval, and p-value
(Week 8 evaluation will only be applicable to patient receiving treatment 2)

4. Quality of life assessment using GERD-HRQL

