Descriptive statistics (mean, standard deviation, median, minimum, and maximum) for the changes from baseline in the total score of quality of life at the first 7 days, 4 weeks, and 8 weeks will be presented by time point. For the changes from baseline in variables measured at the first 7 days, 4 weeks, and 8 weeks after the IP administration, an ANCOVA model including treatment group as treatment effect, baseline values, and stratification factor (based on dominant symptoms in inclusion criteria: experiencing heartburn, regurgitation, or both of them more than >3 days in the last 7 days) as covariate will be applied. The results of ANCOVA model will be summarized as the least squares mean (LSM) and standard error by treatment group, the LSM differences between the study group and the control group, the corresponding 2-sided 95% confidence interval, and p-value. (Week 8 evaluation will only be applicable to patient receiving treatment 2)

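### The model for symptom-free days is an ANCOVA in name only; prespecifying the Visit 2 GERD-Q heartburn and regurgitation items as covariates is nearly free and may add some precision

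*Combined protocol and SAP*

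**What the plan says.** Section 9.2.3.2 plans three models for continuous secondary endpoints.

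- **Symptom-free days (item 2):** "an ANCOVA model will be applied with treatment group as a treatment effect". The synopsis uses the same words. No other term is named.
- **GERD-Q change in symptom frequency (item 3):** "an ANCOVA model including treatment group as treatment effect, and baseline value will be applied".
- **GERD-HRQL change in total score (item 4):** "an ANCOVA model including treatment group as treatment effect, baseline values, and stratification factor", the last being the dominant-symptom group from the inclusion criteria.

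On what is known before treatment, section 8.3.3 says of the GERD-Q: "The subject will complete the GERD-Q at the screening visit (Visit 1) and Visit 2". Of the GERD-HRQL it says that subjects "will complete the GERD-HRQL questionnaire at Visit 2, Visit 3, Visit 4 and Visit 5". The diary, which supplies the endpoint, starts later. Section 8.3.14 says: "The subject diary will be distributed at Visit 2 and the training on how to complete it will be provided". Section 8.3.13 starts dosing the day after dispensing: "For maximum 8 weeks from the next day of investigational product dispensing".

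The plan gives no reason for leaving covariates out of the diary model.

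**The concern.** A model whose only term is treatment is a one-way ANOVA with two groups, that is, a two-sample t-test. The least squares mean differences it is meant to report are then the raw mean differences. The label promises an adjustment that the text does not specify.

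Two things follow. First, some precision may be given up on the endpoint where the phase 2 study showed a difference from esomeprazole (section 1.4), in a trial planned on 53 evaluable subjects per arm. Second, an ANCOVA without a named covariate leaves the choice of covariate to be made later, in an open-label trial. The endpoint covers three symptom definitions, three windows and three times of day (3 × 3 × 3 = 27 possible comparisons), so that choice should be closed in advance.

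**Working it through.** **1. The plan's own figure.** No precision or power is stated for this endpoint. The only sample size is for the primary endpoint (section 9.4.2): 88.5% against 94.0%, margin -0.1, one-sided 2.5%. With 53 per group and pooled variance:

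- null SE = √(2 × 0.9125 × 0.0875 / 53) = 0.0549
- alternative SE = √((0.885 × 0.115 + 0.94 × 0.06) / 53) = 0.0546
- power = Φ((0.155 − 1.96 × 0.0549) / 0.0546) = 0.807, as printed in the plan
- 53 / 0.8 = 66.25, rounded up to 67 per arm, or 134 in total

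This reproduces, and nothing below changes it.

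**2. Is a relevant covariate available?** The first two items of the GERD-Q form (Attachment 2) ask on how many of the last 7 days the subject had heartburn and regurgitation. These are the two symptoms that the diary scores (section 8.4.2.2). They are recorded at Visit 2, before the first dose.

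**3. How much can those items vary?** Each has four levels: 0, 1, 2-3 and 4-7 days, scored 0 to 3. Inclusion criterion 2 requires more than 3 days of heartburn or of regurgitation. At qualification, therefore, at least one item is at its top score in every subject, and both are in subjects who have both symptoms often. Only the non-qualifying item is free to vary. This may keep the correlation with the outcome low.

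**4. Size of the gain.** Let R be the (multiple) correlation of the two items with the outcome within arms. Residual variance is multiplied by 1 − R², and interval width by √(1 − R²). R is not in the documents; the range below is assumed.

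The last two columns are an illustration. They use an SD of 38.7 points, back-calculated from the phase 2 7-day result: 43.98% − 28.27% = 15.71 points, p = 0.0463. This assumes a t-test with the 51 and 48 subjects given for the healing analysis. Then t ≈ 2.02, SE = 15.71 / 2.02 ≈ 7.78, and SD = 7.78 / √(1/51 + 1/48) ≈ 38.7. The half-width is 1.96 × 38.7 × √(2/53) × √(1 − R²).

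| R (assumed) | Variance reduction | Width reduction | 95% half-width, points | Power for 15.71 points |
|---|---|---|---|---|
| 0 | 0% | 0% | 14.7 | 55% |
| 0.1 | 1% | 0.5% | 14.7 | 56% |
| 0.2 | 4% | 2.0% | 14.4 | 57% |
| 0.3 | 9% | 4.6% | 14.1 | 59% |
| 0.5 | 25% | 13.4% | 12.8 | 68% |

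**5. The price of two slopes.** Residual degrees of freedom fall from 106 − 2 = 104 to 102. For roughly normal covariates, chance imbalance multiplies the variance on average by 1 + 2/(104 − 2 − 1) = 1 + 2/101 ≈ 1.020, or the width by about 1.01. The table leaves this out. At R = 0.1 it cancels the gain (0.995 × 1.01 ≈ 1.005); from R = 0.2 upwards a net gain remains.

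**The case against.** A reader might infer that an adjustment used elsewhere was simply dropped here, so that precision is lost for no reason. The documents do not support that. The GERD-Q and GERD-HRQL models analyse change scores and adjust for the baseline of their own instrument. Symptom-free days is not a change score. With the diary first handed out at Visit 2 and dosing from the next day, no baseline of the same kind exists. That is an evident reason for having no baseline term of the endpoint itself. It is not a reason for having no covariate: a covariate need not be on the outcome's scale, and the dominant-symptom factor in the GERD-HRQL model is not.

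A second tempting reading is that the gain is substantial. It may not be. The correlation is unknown, the covariate is coarse, and eligibility puts part of it at its ceiling. At 0.1 to 0.2 the benefit is negligible.

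A third is that the treatment comparison is biased. It is not, on this account: randomisation protects the unadjusted comparison in the 7-day and 4-week windows. The 8-week window is limited to subjects who go on to Treatment 2, a group selected after randomisation, and adjustment would not cure that.

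Phase 2 support for the endpoint is also partial. Section 1.4 reports no significant difference for 7-day daytime results or for regurgitation alone.

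**Conclusion.** The mismatch between label and model is certain from the text. So is the availability of pre-dose measures of the same two symptoms. The size of the benefit is not known: the interval narrows by about 0.5% to 5% for correlations of 0.1 to 0.3 and by 13% at 0.5, less about 1% for the two slopes. These figures rest on an assumed correlation. The half-widths and powers rest further on an SD inferred from one phase 2 p-value.

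The point is minor but worth correcting. It concerns one secondary endpoint, chiefly at 7 days and 4 weeks. Closing the choice of covariate in advance has value even if the correlation proves low. The primary analysis, its margin and the sample size are not touched.

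**What to change.** In section 9.2.3.2, item 2, and in the matching synopsis text, specify one model for all symptom-free-day outcomes: treatment group plus the Visit 2 GERD-Q heartburn and regurgitation item scores (each 0 to 3, entered as numeric covariates).

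- Do not offer the GERD-HRQL total as an alternative. A choice would leave the model open, and the total is inconsistently defined: section 8.4.2.3 sums 15 questions to a maximum of 75, whereas Attachment 3 shows ten items scored 0 to 5 and a satisfaction question.
- Do not add the dominant-symptom group. It largely repeats which of the two items scores 3.
- Do not present the adjustment as a remedy for the week 8 subset.

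The cost is one sentence in each place and two degrees of freedom. No new data, visits or subjects are needed.
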